THE EFFECT OF INTRAPERITONEAL
INSTILLATION OF BUPIVACAINE ON
POSTOPERATIVE PAIN AFTER SURGICAL
LAPAROSCOPY

ID: 0107909

Date: 4/12/2023

INTRODUCTION

Laparoscopy is an invasive surgical technique used in both diagnostic and operative procedures ,one benefit of laparoscopy is that it usually takes less time and has a faster recovery than open surgery, ⁽¹⁾ postoperative pain as a result of surgical laparoscopy occurs in up to 80% of women, with potential significant morbidity, in form of delayed discharge and readmission. ⁽²⁾

Pain after surgical laparoscopy is due to various causes, such as : trocar insertion stimulating somatic pain receptors in the skin ,chemical irritation of peritoneal nerves due to abdominal distension by CO2 which is transformed into carbonic acid in nerves,⁽³⁾ distention secondary to pneumoperitoneum causes mechanical irritation of visceral and parietal nerves of the peritoneum, furthermore the surgical intervention causing injury and inflammation of the tissues, spillage of blood or serous fluid causing more irritation to the visceral and parietal nerves of the peritoneum which leads to visceral dull aching pain referred mainly to the distribution of the nerve dermatomal area.⁽⁴⁾

Unfortunately, pain is the major complaint of the patients, thus making its evaluation a fundamental requisite in the outcome assessment in our practice. Pain intensity, duration and related disability are the aspects that define pain and its effects. For each of these aspects, different assessment tools exist. ⁽⁵⁾

Visual Analogue Scale (VAS) consists of a straight line with the endpoints defining extreme limits such as 'no pain at all' and 'pain as bad as it could be'

The patient is asked to mark his pain level on the line between the two endpoints. This tool was first used in psychology by Freud in 1923.⁽⁶⁾

McGill Pain Questionnaire by Melzack, (1975) represented a major evolution in pain research thanks to the MPQ, the qualitative aspect of pain became an important subject in pain research. Pain descriptors were categorized

in three dimensions of pain experience: words that described the **sensory** qualities of the experience in terms of temporal, spatial, pressure, thermal, and other properties, words that described **affective** qualities in terms of tension, fear, and autonomic properties that are part of the pain experience, and evaluative words that subjectively described the overall **intensity** of the total pain experience.⁽⁷⁾

There are numerous interventions that are associated with reduction in the incidence, severity or both of pain or a reduction in analgesia requirements for women having surgical laparoscopy for gynecological purposes.⁽⁸⁾ These could be medical or surgical or even technical interventions that has been developed in an attempt to reduce postoperative pain after surgical laparoscopy as an example of those interventions developing a specific technique for releasing pneumoperitoneum; humidification of gas used in pneumoperitoneum reducing the pressure used to inflate the abdomen,⁽⁹⁾ also novel techniques regarding intraperitoneal fluid instillation using isotonic saline; an intra-peritoneal drain in an attempt to eliminate any residual fluid or gas; and local anesthetic applied to the peritoneal cavity to reduce nerve irritation of the peritoneal and visceral nerves.⁽¹⁰⁾

Bupivacaine, is a local anesthetic. In nerve blocks, it is injected around the nerve that supplies a certain area, or into the spinal canal's epidural space,⁽¹¹⁾ bupivacaine binds to the intracellular portion of voltage-gated sodium channels and blocks sodium influx into nerve cells, which prevents depolarization. Without depolarization, no initiation or conduction of a pain signal can occur.⁽¹²⁻¹⁴⁾

Hence the idea of our study is to instill bupivacaine in a certain concentration in the peritoneal cavity in an attempt to reduce postoperative pain after surgical laparoscopy for gynecological purposes that will inflect certainly on patient's hospital stay and mobility.

AIM OF THE WORK

The aim of the present study is to:

Primary

1. Evaluate the efficacy of instilling bupivacaine intraperitoneal in reducing postoperative pain after surgical laparoscopy for gynecologic procedures.

Secondary

1. Assessment of the timing passed postoperative, since the patient needs to start the first analgesic dose.
2. Frequency of analgesia requested by the patient in postoperative period.
3. Assessment of the time passed postoperative since the patient start mobility.

PATIENTS

This randomized controlled trial will be conducted for (80) women undergoing laparoscopic procedures at endoscopy unit at El-Shatby Maternity University Hospital, after approval of ethical committee of Alexandria Faculty of Medicine.

Inclusion Criteria:

- 1- Patients those are indicated for surgical laparoscopy, whatever the gynecological problem.
- 2- Age between (18-50) years.
- 3- Cooperative patient that can express pain and score it.

Exclusion criteria:

- 1- Non-cooperative patients that cannot express and score pain.
- 2- Drug abusers due to altered pain threshold.
- 3- Surgical laparoscopy indicated for oncological procedures.
- 4- Any allergy or reaction to any of the derivatives of bupivacaine drug group.
- 5- Any cardio-pulmonary condition.

Randomization will be through opaque sealed envelopes.

METHODS

After signing their informed consents, the patients who are included in the study will be divided into two groups each group include (60) patients.

Group A: Patients that will receive intraoperative instillation of bupivacaine.

Group B: (Control group) that will not receive the medication.

The patients in both groups will be subjected to:

Pre-operative:

History taking (gynecological, obstetric, medical any drug reaction and surgical), general examination and abdominal examination.

Intra-operative:

premedication : 1.5 microgram/kg fentanyl IV

induction of anesthesia: 2mg/kg Propofol IV , 0.5 mg/kg Atracurium IV , ventilation via face mask 2-3 minutes , then endotracheal intubation

1gm paracetamol IV as intraoperative analgesia which will not interfere with postoperative pain scoring.

Group (A) only will receive intra-peritoneal 40 ml bupivacaine 0.2%, after laparoscopic procedure before removing trocars.

Post-operative (Outcome variables):

- 1- Assessment of the postoperative pain at 2h, 8h ,24h respectively by visual analogue score (VAS).
- 2- Assessment of the timing -in hours- of analgesia initiation postoperatively -when VAS score is 4 or more-, non-steroidal analgesia ketorolac 30 mg will be used.
- 3- Assessment of the frequency of analgesic need postoperatively.
- 4- Assessment of the timing-in hours- of mobility initiation postoperatively.

Every patient will be asked by the data collector, in order to fulfill the following -appendix- sheet postoperative.

ETHICS OF RESEARCH

Research on human or human products:

- Prospective study: Informed consent will be taken from patients. In case of incompetent patients, the informed consent will be taken from the guardians.
- Retrospective study: Confidentiality of records will be considered.
- DNA / genomic material: Informed consent for DNA/genomic test and for research will be taken from patients. No further tests will be carried out except with further approval of committee and patients. If the samples will travel outside Egypt the researcher will be responsible for transportation and security approval.
- All drugs used in the research are approved by the Egyptian Ministry of Health.

Research on animal:

- The animal species are appropriate for the test.
- After test, if the animal will suffer, it will be euthanized and properly disposed.
- After operation, it will have a proper postoperative care.

سأقوم بتسلیم الموناقات المبنیة على علم المريض الخاصة بالدراسة عند الانتهاء منها أو
عند طلبها من اللجنة

RESULTS

The results will be tabulated and statistically analyzed, using the standard statistical methods.

Statistical analysis of the data

Data will be fed to the computer and analyzed using IBM SPSS software package version 20.0. (Armonk, NY: IBM Corp) Qualitative data were described using number and percent. The Kolmogorov-Smirnov test will be used to verify the normality of distribution Quantitative data were described using range (minimum and maximum), mean, standard deviation, median and interquartile range (IQR). Significance of the obtained results will be judged at the 5% level.

The used tests were

1 - Chi-square test

For categorical variables, to compare between different groups

2 - Fisher's Exact or Monte Carlo correction

Correction for chi-square when more than 20% of the cells have expected count less than 5

3 - Student t-test

For normally distributed quantitative variables, to compare between two studied groups

4 - Mann Whitney test

For abnormally distributed quantitative variables, to compare between two studied groups

5 -Wilcoxon signed ranks test

For abnormally distributed quantitative variables, to compare between two periods

DISCUSSION

The results will be discussed in view of achievement of the aim and will be compared with available literature and published data

REFERENCES

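### The SAP gives two incompatible trial sizes: 80 women in total, and two groups of 60 (120 women)

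*SAP*

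**What the plan says.** The PATIENTS section states the total: "This randomized controlled trial will be conducted for (80) women undergoing laparoscopic procedures".

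The METHODS section describes the allocation after consent: "the patients who are included in the study will be divided into two groups each group include (60) patients". It then defines two groups, A (bupivacaine instillation) and B (control without it). No third group is described.

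The only other statement about allocation is at the end of the exclusion criteria: "Randomization will be through opaque sealed envelopes". It gives neither the number of envelopes nor a ratio. The statistical section sets the significance level ("Significance of the obtained results will be judged at the 5% level") and lists the two-group tests, but gives no sample size of its own.

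**The concern.** Two groups of 60 make 120 women, not 80. The sample size determines when recruitment stops, when the data are analysed and what difference the trial can detect. With two written targets, stopping at 80 and continuing to 120 could each be described as following the plan. The text therefore does not rule out analysing at 80 and then carrying on. Nothing suggests that anyone intends this, but a plan should exclude it. A reader of the eventual report would also have no single planned number against which to judge whether the trial was completed.

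**Working it through.** **Inputs from the SAP**

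- Total: 80 women (PATIENTS).
- Groups: two, of 60 each (METHODS). Equal allocation is implied by the equal group sizes.
- Significance level: 5%, sidedness not stated (statistical section).
- Test: Student t-test, or Mann-Whitney if the data are not normal (statistical section).
- Effect size, SD, target power and dropout allowance: not given.

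**Step 1: can the two figures agree?**

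- Groups × size per group = 2 × 60 = 120, against a stated 80.
- In the other direction, 80 / 2 = 40 per group, against a stated 60.
- Gap: 120 − 80 = 40 women, and 40 / 80 = 50%. This is not rounding.

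**Step 2: could a dropout allowance link them?**

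Recruiting 120 to retain 80 requires a loss of 1 − 80/120 = 33.3%. For comparison, 10% dropout would give 80 / 0.90 = 89 (rounded up), and 20% would give 80 / 0.80 = 100. No allowance is stated, and the last scheduled pain score is at 24 hours. A distinction between screened and randomised women does not help either: the larger number is the one allocated after consent and inclusion, and 80 women cannot yield 120 allocated.

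**Step 3: what changes between the two sizes?**

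Assumptions: two-sided 5% level, equal groups, t-test, differences expressed in SD units because the SAP gives no SD.

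The detectable difference by the normal approximation is d = (z₀.₉₇₅ + z_power) × √(2/n), with n per group. At 80% power:

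- n = 40: (1.960 + 0.842) × √(2/40) = 0.63 SD
- n = 60: (1.960 + 0.842) × √(2/60) = 0.51 SD

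The exact t-test calculation gives 0.634 and 0.516 SD. The power figures below also use the exact t-test.

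| Assumed true difference | Power, 40 per group | Power, 60 per group |
|---|---|---|
| 0.4 SD | 42% | 58% |
| 0.5 SD | 60% | 78% |
| 0.6 SD | 76% | 90% |
| 0.7 SD | 87% | 97% |

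The width of the confidence interval is proportional to √(2/n), so the ratio is √(60/40) = 1.22: the interval is 22% wider with 40 per group.

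**Step 4: a conditional illustration**

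Suppose the data were tested at 80 women and, if not significant, again at 120, each time at an unadjusted 5%. The two test statistics have correlation √(80/120) = 0.816, and the chance of at least one false positive is 7.7%. The plan does not call for this; the figure shows only what an open stopping point could cost.

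**The case against.** The contradiction itself is hard to dispute. Both numbers stand in complete sentences, there is no amendment log that would make one of them superseded text, and nothing is redacted nearby. The objections concern how much to make of it.

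- *Power would be unstated even with one agreed size.* This is right. The SAP gives no effect size, SD or target power, and a justification may lie in a protocol that is not shown, so its absence is not counted here. The contradiction leaves the target and the stopping point open; its effect on power is that the detectable difference depends on which figure holds.
- *The 7.7% error rate is hypothetical.* Also right. The SAP mentions no interim look, and a drafting slip in one number is the likelier explanation. The figure applies only if both looks are taken.
- *Two-sided testing, 80% power and 0.5 SD are the reviewer's choices.* They are, which is why a range is shown. At 0.7 SD both sizes have power above 85% and the practical gap is smaller. Mann-Whitney results would differ somewhat from the t-test figures.
- *The protocol may settle the matter.* It could show which number was intended, but one sentence of the SAP would still be wrong.

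None of these points makes 80 and 120 compatible.

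**Conclusion.** The point holds and must be fixed. The SAP states a core design figure in two ways that differ by 40 women, a factor of 1.5, and no reading of the document reconciles them. That conclusion rests on arithmetic alone and needs no assumption. The size of the consequence does rest on assumptions (two-sided 5%, t-test, equal groups): at 80% power the detectable difference moves from 0.63 SD to 0.52 SD, and over true differences of 0.4 to 0.7 SD power runs from 42% to 87% with 40 per group and from 58% to 97% with 60.

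**What to change.** State one size in both sections:

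- if 80 is the intended total, change the group size in METHODS from 60 to 40; or
- if 60 per group is intended, change the total in PATIENTS from 80 to 120.

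The document does not show which is right. The sponsor should decide from the approved or planning record, and without reference to outcome data if recruitment has begun.

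Two additions would help, although they go beyond correcting the error: state the difference the chosen size can detect (0.63 SD or 0.52 SD at 80% power, under the assumptions above), and state that there is a single analysis once that number is reached.

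The edit is one number in one sentence. Keeping 80 needs no extra patients, at the price of the larger detectable difference. If 120 is intended the edit is just as small, but the document does not show whether approvals or recruitment were based on 80, so that would have to be checked.

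### Groups are formed straight after consent although the arms differ only at the end of surgery; the SAP should fix the opening of the envelope at that later point

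*SAP*

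**What the plan says.** Under PATIENTS, after the exclusion criteria, the SAP gives the allocation method: "Randomization will be through opaque sealed envelopes". It gives no moment of opening.

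METHODS then places the division into groups directly after consent: "After signing their informed consents, the patients who are included in the study will be divided into two groups". Group A is to receive bupivacaine during the operation. Group B is an untreated control.

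Next comes a list introduced by "The patients in both groups will be subjected to". Its pre-operative part is "History taking (gynecological, obstetric, medical any drug reaction and surgical), general examination and abdominal examination". Its intra-operative part gives the premedication, induction and paracetamol for both groups. The only step that separates the arms closes that part: group A alone has the instillation, "after laparoscopic procedure before removing trocars".

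The SAP describes no placebo instillation and no masking of patient, surgeon, anaesthetist or data collector.

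**The concern.** In an open comparison with an untreated control, each step carried out after the arm is known is a step that knowledge of the arm can influence. Here the groups are formed before the entire operation, yet the treatment difference arises only at its end. Two things follow.

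First, if the envelope is opened when the groups are formed, the operating team works with a known arm. The SAP's own INTRODUCTION names techniques in the surgeon's hands that have been used to reduce pain after laparoscopy, among them "an intra-peritoneal drain in an attempt to eliminate any residual fluid or gas". A difference between arms in how surgery was conducted, even an unintended one, would enter the VAS comparison and could not be separated from the drug effect.

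Second, a woman whose laparoscopy is converted to open surgery or abandoned would already belong to an arm. Either she is dropped after allocation, or she is analysed without having reached the step that the trial compares. The section on statistical analysis does not say which.

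**Working it through.** No figure in the SAP bears on this point, so the check is of sequence. The order as printed in METHODS, with the follow-up from its outcome list:

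1. Consent is signed.
2. Women are divided into groups A and B.
3. History and examination, both groups.
4. Premedication, induction and paracetamol, both groups.
5. The laparoscopic procedure, both groups.
6. Instillation, group A only.
7. Trocars are removed.
8. VAS at 2, 8 and 24 hours.

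**Does anything in steps 3 to 5 depend on the arm?** No. The SAP gives the same work-up and the same anaesthetic drugs to both groups, and the first difference is step 6. Moving allocation from step 2 to the gap between steps 5 and 6 therefore takes nothing away from the treatment described.

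**What is exposed at each possible opening time?** If the envelope is opened at step 2, steps 3, 4 and 5 can all take place with the arm known. If it is opened between steps 5 and 6, none of them can. The SAP fixes only the moment at which groups are formed (step 2) and not the moment of opening, so the first case is allowed by the text but not stated.

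**Who is allocated without reaching step 6?** With allocation at step 2, this is every woman whose procedure is converted or abandoned during step 5. With allocation after step 5, it is none of them. The SAP gives no rate for such events.

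**Can the effect on VAS be sized?** No. It would need the shift in mean VAS caused by unequal surgical conduct and the standard deviation of VAS, and the SAP gives neither. Assumed values show why an invented one does not help. With shift d, standard deviation s, n per group and no drug effect, a two-sided 5% t-test has noncentrality d / (s × √(2/n)). Take s = 2 and n = 40, which is half of the 80 women under PATIENTS:

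- d = 0.5: 0.5 / (2 × √0.05) = 1.12, and the test is significant in about 20% of trials.
- d = 0.2: 0.2 / (2 × √0.05) = 0.45, about 7.3%.
- d = 0.1: 0.1 / (2 × √0.05) = 0.22, about 5.6%.

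With the 60 per group given in METHODS, the same three shifts give about 27%, 8.4% and 5.8%. The answer runs from almost nothing above the nominal 5% to several times that level, depending wholly on the assumed shift. It carries no information about this trial.

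**The case against.** The strongest reply is that the SAP nowhere says that anyone knows the arm during surgery. Sealed envelopes conceal the assignment until they are opened, and the opening time is simply not given. This stands. A reader might infer that allocation is known throughout the operation. The document supports only that it may be, because groups are formed early and no later opening is specified.

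A reader might also infer that eligibility is settled with the arm known, because the history and examination that could reveal "Any allergy or reaction to any of the derivatives of bupivacaine drug group" or "Any cardio-pulmonary condition" are listed after the division. The text does not support this as a finding. METHODS divides patients who are already included in the study, which implies that eligibility came first, and the later list can be read as care common to both groups. Stating that order outright is still worthwhile, but as a clarification.

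Nor should one infer that women found during surgery to have oncological disease would be excluded after allocation. That exclusion concerns the indication for laparoscopy, which is known beforehand.

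It can be said too that randomising consented, included patients before surgery is ordinary practice, that the techniques in the INTRODUCTION are background, and that surgical detail may sit in a protocol not at hand. All of this is fair. Nothing in the SAP shows that technique varies by arm, and the absence of surgical detail is not the point made here. The point rests on what METHODS does fix: group formation at consent, an untreated control, and a single difference at the end of surgery.

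Finally, late opening is not a complete remedy. Trocar removal and everything after it still follow disclosure. That is correct and limits what the change can claim.

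**Conclusion.** The point holds as a cheap improvement to the design, not as a demonstrated bias. METHODS forms the groups before the listed work-up and the whole operation, although the arms differ only in the closing instillation. With an untreated control, no masking described and no opening time given, the arm may be known to the operating team during surgery, and women whose laparoscopy is converted or abandoned would already be allocated.

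The size of any effect on the VAS comparison cannot be derived from the document. The conclusion rests on the printed order of METHODS, and on the assumption that no text elsewhere fixes a later opening of the envelope. If the protocol does so, the SAP need only be brought into line with it.

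**What to change.** Reword METHODS in a sentence or two:

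- History, examination and the eligibility check are completed before allocation.
- The sealed envelope is opened in theatre only when the laparoscopic procedure is finished and the trocars are still in place.
- Women who do not reach that point, for example because the procedure is converted or abandoned, are not randomised.

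The same envelopes serve, and no extra staff or visits are needed. The small cost is that an envelope must be available and handled in theatre at the end of each case. The change closes the route to bias before instillation. It leaves untouched whatever arises afterwards from the untreated control and the absence of masking, and the plan should not present it as a cure for that.

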APPENDIX

Evaluation sheet of post-operative pain

Patient name:

Date:

Registration number:

Mobile number:

Operation undergone:

[figure not shown]
Time exiting the OR:

Time of first analgesia:

[figure not shown]
Frequency of analgesia:

Time of first mobility:

[figure not shown]
2h. post-operative (.....)

8h. post-operative (.....)

24h. post-operative (.....)

No pain (0), Mild (1-3), moderate (4-6), severe (7-9), worst pain (10), start analgesia at threshold -moderate pain- which is score 4.

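### The SAP does not fix which VAS comparison (2, 8 or 24 h) decides its only primary aim, so a mixed result could be reported as success or as failure

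*SAP*

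**What the plan says.** AIM OF THE WORK gives one primary aim: "Evaluate the efficacy of instilling bupivacaine intraperitoneal in reducing postoperative pain after surgical laparoscopy for gynecologic procedures". It names no time, statistic or target difference.

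METHODS, Post-operative (Outcome variables), item 1 supplies the only pain outcome: "Assessment of the postoperative pain at 2h, 8h ,24h respectively by visual analogue score (VAS". Items 2 to 4 (time to first analgesia, frequency of analgesia, time to mobility) match the three secondary aims. VAS is therefore the primary outcome by elimination, although it is not labelled as such.

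Statistical analysis of the data lists the Student t-test ("For normally distributed quantitative variables, to compare between two studied groups") and the Mann-Whitney test ("For abnormally distributed quantitative variables, to compare between two studied groups"), with normality checked by Kolmogorov-Smirnov. The only statement on error is "Significance of the obtained results will be judged at the 5% level". The Wilcoxon signed ranks test, also listed, compares two periods; it neither compares the groups nor combines the three times. The listed means, medians and ranges are descriptive.

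The DISCUSSION section adds only this: "The results will be discussed in view of achievement of the aim". What counts as achievement is not defined.

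**The concern.** Three VAS comparisons serve one primary question, and the plan does not say how three answers become one conclusion. Suppose the groups differ at 2 h but not at 8 h or 24 h. One analyst could report that bupivacaine reduced pain and another that the aim was not met, and both would have followed the SAP. The verdict can then be chosen after the data are seen.

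The meaning of the 5% level is also at stake. It applies to the obtained results in general and is tied to no comparison, so the error rate for the primary question depends on a rule that is not written down.

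**Working it through.** **Inputs from the SAP.** Three VAS times (METHODS, item 1); 5% level (Statistical analysis of the data). Sidedness is not stated; two-sided is assumed, critical value 1.960.

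**Assumed inputs.** The SAP gives no correlation between VAS times, no SD and no effect size. Equal correlation ρ between all pairs of times is assumed, at 0.3, 0.5 and 0.8. For the case of a real effect, 80% power at each time is assumed (shift δ = 1.960 + 0.842 = 2.802). Sample size does not enter these calculations, so the SAP's two figures for it (80 women in all, 60 per group) do not affect them. The 5% is a stipulated level, so there is no figure of the plan's own to reproduce.

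**Model.** Write each test statistic as Z = δ + √ρ·u + √(1−ρ)·e, with u shared by the three times. Given u, each time is significant with probability p(u). Then, integrating over the standard normal density φ(u):

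- P(none) = ∫ (1−p(u))³ φ(u) du
- P(any) = 1 − P(none)
- P(all) = ∫ p(u)³ φ(u) du
- P(mixed, one or two of three) = P(any) − P(all)

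Check at ρ = 0: P(any) = 1 − 0.95³ = 0.1426.

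**Results** (last-digit differences are rounding):

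| | ρ = 0.3 | ρ = 0.5 | ρ = 0.8 |
|---|---|---|---|
| No effect: any | 0.1362 | 0.1254 | 0.0982 |
| No effect: all | 0.0009 | 0.0032 | 0.0141 |
| No effect: mixed | 0.1354 | 0.1222 | 0.0842 |
| 80% power each: any | 0.9714 | 0.9499 | 0.8995 |
| 80% power each: all | 0.5698 | 0.6114 | 0.6866 |
| 80% power each: mixed | 0.4016 | 0.3386 | 0.2129 |

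**Any-time rule.** The false-positive rate is the first row: 13.6%, 12.5%, 9.8%. It is 14.3% at ρ = 0, 8.4% at 0.9 and 7.3% at 0.95, and it tends to 5% as ρ nears 1. Counting only false claims of benefit, the rates are 6.8%, 6.3% and 4.9% against 2.5%.

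**All-three rule.** The worst case is no effect at one time and very large effects at the other two; the error is then 0.0500 at every ρ. If those two times have 80% power, it is 0.0312, 0.0289 and 0.0254. Error is controlled.

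**Bounded scores.** In simulation with scores rounded to 0–10 (assumed mean 4, SD 2, no effect, 40 or 60 per group, 20,000 trials per setting), the any-time rate over the same three correlations ran from 9.9% to 14.0% for the t-test and the Mann-Whitney test. This agrees with the normal model.

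**Holm's first step.** The level is 0.05/3 = 0.0167, critical value 2.394. An effect with 80% power at 5% has P(Z > 2.394 − 2.802) = 0.658. Keeping 80% needs ((2.394 + 0.842)/(1.960 + 0.842))² = 1.33 times the patients.

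**The case against.** Only the SAP is at hand, and a protocol may name a lead time. The primary question would then rest on one test, no adjustment would be needed, and a mixed result would raise no dispute. That is fair, and it limits the point to what this document fixes. Even so, the SAP ties its 5% level to no comparison and refers to no lead time set elsewhere.

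A reader might infer that the SAP tests each time at 5% and accepts any one significant time, so that its true error is 10% to 14%. The text does not say so. It leaves that reading open, but equally leaves open the all-three rule, under which error does not exceed 5%. The inflation belongs to one reading and is shown here only as an illustration.

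Two supports that might be offered are weak. The evaluation sheet in the APPENDIX lists the three times alike ("2h. post-operative" and so on), but a data-collection form would not normally mark a primary time. The INTRODUCTION says "Pain intensity, duration and related disability are the aspects that define pain and its effects"; that is general background and does not make an unweighted mean of scores at 2, 8 and 24 h the natural summary.

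The SAP also lists chi-square and Fisher tests, and the APPENDIX grades the VAS, so a categorical comparison is not excluded. This widens the choice and does not settle it. The score of 4 is a trigger for analgesia and is not a success criterion.

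**Conclusion.** The point stands as an ambiguity in the decision on the only primary aim. It needs no assumption about which success rule was meant, and it should be settled before the data are seen, because it cannot be credibly settled afterwards.

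Its practical weight is that a mixed result is a likely event: about one trial in five to two in five if each time has 80% power, and about one in twelve to one in seven with no effect. The unwritten rule then decides the outcome. At ρ = 0.5 and 80% power per time, an any-time rule succeeds in 95% of trials and an all-three rule in 61%. These sizes rest on equal correlation between times, the assumed power and two-sided tests; the gap in the text does not. The documents do not support saying that the plan has a fixed error rate above 5%.

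**What to change.** Before the data are seen, write one of these into Statistical analysis of the data:

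1. One named VAS time is the single primary comparison of group A with group B, at two-sided 5%, with the reason for choosing it. The other two times are secondary.
2. All three times stay primary with Holm (smallest p against 0.0167, next against 0.025, last against 0.05), and success means at least one Holm-significant time.

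Under either option:

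- Fix one test in advance, for example the Mann-Whitney test already listed. Leaving the choice to the Kolmogorov-Smirnov result keeps part of the primary analysis dependent on the data.
- State how VAS scores recorded after rescue analgesia enter the comparison, since the SAP provides for ketorolac once the score reaches 4 and later scores may reflect it.

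The change is to wording only; no measurement is added. Under option 1, an isolated p < 0.05 at a non-primary time no longer counts as success. Under option 2, at Holm's first step, an effect confined to one time with 80% power falls to about 66%, or needs about 33% more patients to stay at 80%.
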